### 9.3.4 Other Reporting

Any Serious Adverse Event, as described in Section [9.3.1](#), including death due to any cause, which occurs during this study must be reported immediately (within 24 hours) to the ABTC Central Office.

A phone call must be made to:

#### **9.4 Data Reporting**

This study will be monitored by the Clinical Data Update System (CDUS). The ABTC Central Office is responsible for compiling and submitting CDUS data to CTEP for all participants and for providing the data to the Principal Investigator for review. Cumulative CDUS data will be submitted quarterly to CTEP by electronic means. Reports are due January 31, April 30, July 31 and October 31.

## 9.5 Correlative Studies

Table 9.5: Synopsis of Correlative Studies

Measurement	Technique	Participants	Timing of collection	Collection requirements	More Information
EGFR gene amplification in Tumor: ( Integral Biomarker )	Fluorescence In-Situ Hybridization (FISH) on FFPE	Group A and Reference Group	Archived sample	5 UNSTAINED SLIDES (4 micron thick) from most recent surgery	Section 9.5.2
Ki67 and other IHC measurements ( Exploratory )	IHC of FFPE tumor tissue	Group A and Reference Group	Archived and protocol surgery	20 UNSTAINED SLIDES each from archived tumor block and protocol surgery tumor block: 5 micron thick	Section 9.5.2
Lapatinib blood concentrations ( Exploratory )	LC-MS/MS analysis of plasma samples	Group A	Before and During Protocol surgery	Three BLOOD SAMPLES : one sample collected before starting lapatinib and two samples collected during tumor resection	Section 9.5.3
Lapatinib tumor concentration ( Integrated )	LC-MS/MS analysis of fresh frozen tissue	Group A	Protocol Surgery	Combined Total Tumor Tissue Required for both tumor concentration and EGFR phosphorylation ( FROZEN TUMOR SPECIMEN WILL BE SPLIT INTO ALIQUOTS AT CENTRAL SITE ):	Section 9.5.5
EGFR phosphorylation in Tumor ( Integrated )	Electro-chemiluminescence of fresh frozen tissue	Group A and Reference Group	Protocol surgery	At least 500mg from contrast enhancing region. When possible, also at least 100 mg from non-contrast enhancing region	Section 9.5.6
Ex-vivo sensitivity of tumor sphere cultures ( Exploratory )	Trypan Blue Assay	Group A and Reference Group	Protocol Surgery	When possible, 500 mg or more of additional Tumor Tissue for Tumor Sphere Culture	Section 9.5.7

Biospecimen Criteria for Patient Replacement: patients on protocol will be replaced if any of the following tissue factors apply:

Surgical sample:

- Less than 500 mg of frozen tissue obtained from the contrast enhancing portion of the tumor
- Frozen tissue does not contain tumor
- Time from tumor removal to freezing greater than 5 minutes
- No paraffin tumor block or fewer than 20 unstained slides available.

Archived surgical sample:

- Fewer than 20 unstained slides available

Blood PK (applies to Group A only):

- Blood samples not obtained at time of surgery

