### 9.5.1 Tissue Requirements for Protocol Surgery: Group A and Reference Group

Every effort should be made to collect adequate amounts of tissue.

The minimum **tissue requirements** to be collected from participants at the time of surgery include:

- 500 mg of fresh frozen tissue from the contrast enhancing portion of the tumor. This sample will be used for the determination of the primary objectives of the study for both the tumor drug distribution endpoints ([Section 9.5.5](#)) and EGFR phosphorylation endpoints ([Section 9.5.6](#))
- 100 mg of fresh frozen tissue from the non-contrast enhancing portion of the tumor (if low risk of inducing neurological injury). This sample will be used in an exploratory fashion regarding tumor drug distribution and EGFR phosphorylation.
- If sufficient tissue is available, 500 mg or more of additional enhancing tissue (for tumor sphere cultures)

The **remainder of the sample** should be fixed in formalin and processed for routine paraffin embedding and sectioning at the site, per usual site protocols in pathology.

The precise location in the tumor from which these specimens were obtained and the precise time should be recorded. Depending on local site's capabilities, if a common navigation system is used for surgical localization, segmentation of the tumor using 3D visualization software is recommended for accurate sampling localization. Using this

reconstructed model, a representative screenshot is requested demonstrating the location of the resected tissue. If not possible, then a screenshot of the MRI showing the location of the resected tissue should be included.

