**Ship all frozen tumor samples to:**

[name]  
Memorial Sloan Kettering Cancer Center  
[name]  
[name]  
[name]  
Telephone: + 1 [contact]  
Fax: + 1 [contact]

Once specimens arrive at the [name] laboratory, they will be immediately placed at -80°C (or lower). [name] group will collect all samples, cut a 5 µM section from each specimen and then perform H&E staining. Histopathological review of the H&E stain will be performed by a board-certified neuropathologist at Memorial Sloan-Kettering Cancer Center. Only samples with a tumor cell content > 80 % as determined by a pathologist will be used for further analyses. Each frozen tumor specimen that

passes histopathological Q/C will be split into two samples, one for the determination of intratumoral lapatinib concentrations (Section [9.5.5](#)) and one for the determination of EGFR phosphorylation (Section [9.5.6](#)).

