### **9.5.5 Tumor Samples for Intratumoral Drug Distribution: Group A**

The specimens for the determination of intratumoral lapatinib concentration will be shipped to the ABTC Pharmacokinetics Center by the [name] Laboratory following the shipping guidelines in Section [9.5.3](#). The concentration of lapatinib in study samples will be determined by the ABTC Pharmacokinetics Center using an LC-MS/MS assay, also described in Section [9.5.3](#).

Biopsy specimens selected for drug concentration measurement should be at least 0.05 cm^3 (50 mg) intact sections of tumor tissue. To the extent possible, at least one biopsy sample should be resected from a contrast enhancing region of the tumor and another from a non-contrast enhancing region for drug level analysis. These samples must be clearly identified accordingly.

Intratumoral lapatinib concentrations will be measured in fresh frozen tumor aliquots in two batches.

- the first batch of samples (patients # 1-8) will be used for the interim futility analysis and will be run after the initial eight patients. Study enrollment will continue if three or more of these eight tumor samples show an intratumoral lapatinib concentration of > 1.5 μM.
- the second batch of tumor samples (patient # 9-18) will be performed after enrollment has been completed.

Lapatinib concentrations in plasma at the time of tumor resection will also be determined (Section [9.5.3](#)) and this data will be used to calculate a lapatinib tumor/plasma ratio.

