### Primary Objectives and Sample Size:

The first primary objective is to evaluate whether pulsatile lapatinib, when given on the pulsatile dosing schedule, can reach an intratumoral concentration of 1.5  $\mu\text{M}$  or higher in 70% of patients with recurrent and surgically accessible EGFR-amplified high-grade glioma.

Initially eight patients will be treated with pulsatile lapatinib and the intratumoral concentration of lapatinib will be analyzed.

- if no more than 2 patients achieve adequate tumor lapatinib concentration of 1.5  $\mu\text{M}$  or higher, the trial will be stopped early for futility. The probability of early stopping for futility is 68% with a true null of 25% while maintaining only 1.1% probability of early termination for a true rate of 70% (the target).
- if 3 or more of the initial 8 patients reach an intratumoral drug concentration level of 1.5  $\mu\text{M}$  or higher, 10 additional patients will be enrolled into the study.
- if 8 or more of the 18 patients treated with pulsatile lapatinib achieve intratumoral lapatinib concentrations of at least 1.5  $\mu\text{M}$ , the PK objective will be met. This

design has 98% power to detect a true rate of 70% from a null of 25% in achieving lapatinib intratumoral concentration level of 1.5  $\mu$ M with a false positive rate of 0.05.

The PD study will be pursued after the initial 8 patients' PK objective is met.

The primary PD objective is to test the hypothesis that 70% of patients will achieve 80% reduction in ratio of phosphorylated to total EGFR after pulsatile lapatinib treatment assuming a null of 25% patients. A ratio of pEGFR/total EGFR at 80% reduction from a median value from the untreated reference group will be considered as the putative threshold to qualify a near complete inhibition of EGFR (at 80%). If at least 9 (50%) of the 18 treated patients demonstrate a pEGFR/total EGFR ratio which corresponds to at least an 80% reduction compared to the median pEGFR/total EGFR ratio for the 15 patients enrolled on the reference arm, the PD objective will be met. This design yields 98% power to detect a true 70% rate of near complete (80%) EGFR inhibition and it yields a false positive rate of 2% for a true 25% rate of such EGFR inhibition.

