Initial safety monitoring: All adverse events will be monitored and collected throughout the trial and documented based on CTCAE version 5.0. If there are three or more delays of scheduled surgery due to lapatinib-related Serious Adverse Events among the initial 8 patients; or if there are any surgical complications and delayed wound healing SAEs grade  $\geq 3$  considered lapatinib-related among the first three patients, ABTC investigators will consult with CTEP investigators and the pharmaceutical sponsor about such events. An internal safety monitoring evaluation will be conducted after the first three patients complete their first follow-up visit after surgery.

Reference Group (for primary PD study):

15 lapatinib-naïve patients with recurrent and surgically accessible EGFR-amplified high-grade glioma will be enrolled as a reference group for the PD evaluation to establish the threshold of 80% reduction in the ratio of pEGFR/total EGFR. After the initial 8 patients are enrolled into Group A, eligible patients will be sequentially assigned to either treatment group or reference group. The sample size of 15 patients on the reference arm yields 90% confidence that the observed median falls between the true 30th and 70th percentiles of the pEGFR/total EGFR distribution for untreated patients.

To avoid batch effect and other variations through tumor sample processing, all tumor samples will be processed at the same time at the [name] Lab, Memorial Sloan-Kettering Cancer Center.

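### Frozen tumour at or below 80% tumour cells yields no co-primary result, yet on tumour content a patient is replaced only if no tumour is present, so 8, 18 and 15 evaluable patients are not assured

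*Combined protocol and SAP*

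**What the plan says.** - **Histology check (Section 9.5.4, repeated in Appendix III).** "Only samples with a tumor cell content > 80 % as determined by a pathologist will be used for further analyses". Each frozen specimen that "passes histopathological Q/C will be split into two samples, one for the determination of intratumoral lapatinib concentrations" and one for EGFR phosphorylation. A specimen that fails goes to neither assay.
- **Tissue for the endpoints (Section 9.5.1).** Of the 500 mg of contrast-enhancing frozen tissue the protocol says: "This sample will be used for the determination of the primary objectives of the study". Non-enhancing tissue is exploratory.
- **Replacement (Section 9.5).** On tumour content the only trigger is "Frozen tissue does not contain tumor". The other triggers are under 500 mg of enhancing tissue, more than 5 minutes to freezing, too few slides or no block, and (Group A) missing blood samples at surgery. Section 4.1 adds too few doses and more than 12 hours since the last dose, and Section 5.1 adds pre-surgical dosing delayed or stopped for toxicity.
- **Decision rules (Sections 9.5.5 and 11).** At the interim, "the first batch of samples (patients # 1-8) will be used for the interim futility analysis", and enrolment continues with 3 or more of 8. The PK objective is met "if 8 or more of the 18 patients treated with pulsatile lapatinib achieve intratumoral lapatinib concentrations" at the threshold. For PD: "If at least 9 (50%) of the 18 treated patients demonstrate a pEGFR/total EGFR ratio" at the required reduction. For the threshold itself: "The sample size of 15 patients on the reference arm yields 90% confidence that the observed median falls between" the 30th and 70th percentiles.
- **Not stated.** Section 11 does not define an evaluable patient, does not say how a patient without a result counts, and adds no margin to the sample sizes.

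**The concern.** The check for entering the assays and the trigger for replacement use different thresholds. Tissue with some tumour, but not more than 80%, falls between them: it is barred from both assays, yet the patient keeps a place among the 8, 18 or 15. None of the other triggers covers this case. The 500 mg rule, for example, concerns tissue obtained at surgery, not tissue that passed histology.

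The list also looks unbalanced. It replaces a patient with fewer than 20 archived slides, which serve exploratory staining, but not one who has lost both primary results.

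At stake are the power of both primary objectives, the risk of stopping an adequate regimen at the interim, and the precision of the reference median that sets the PD threshold. A second gap follows: with fewer than 18 PD results, the protocol does not say whether the count of 9 or the 50% governs.

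**Working it through.** **Inputs from Section 11.** Null rate 25%, target rate 70%. Interim: stop at 2 or fewer of 8. PK: 8 or more of 18. PD: 9 or more of 18. Reference group: 15.

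**Assumptions.** The documents give no failure rate. I take a patient-level failure rate f of 5% and 10%, independent of drug level and of EGFR inhibition. Failure here means that no enhancing specimen passes.

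**Step 1: reproduce the plan (f = 0), exact binomial.**
- Futility stop, P(Bin(8, p) ≤ 2): 67.9% at p = 0.25 and 1.1% at p = 0.70. Stated: 68% and 1.1%.
- PK two-stage, the sum over x = 3 to 8 of P(Bin(8, p) = x) × P(Bin(10, p) ≥ 8 − x): 0.0498 at 0.25 and 98.5% at 0.70. Stated: 0.05 and 98%.
- PD, P(Bin(18, p) ≥ 9): 1.9% at 0.25 and 97.9% at 0.70. Stated: 2% and 98%.
- Reference median between the 30th and 70th percentiles, P(Bin(15, 0.7) ≥ 8) − P(Bin(15, 0.3) ≥ 8): 90.0%. Stated: 90%.

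All stated figures reproduce when every patient is evaluable.

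**Step 2: chance that nobody is lost, (1 − f)^n.** At f = 5%, all 8 / 18 / 15 are evaluable with probability 66% / 40% / 46%. At f = 10% it is 43% / 15% / 21%.

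**Step 3: counts kept, missing result counted as not meeting the threshold.** The success probability becomes p(1 − f), that is 0.665 and 0.63 at a true 70%, and 0.2375 and 0.225 at a true 25%.

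| Quantity | Stated | f = 5% | f = 10% |
|---|---|---|---|
| PD power | 98% | 95.5% | 91.5% |
| PK power | 98% | 97.0% | 94.5% |
| Wrongful futility stop | 1.1% | 2.0% | 3.4% |
| PD false positive | 2% | 1.4% | 1.0% |
| PK false positive | 0.05 | 0.038 | 0.028 |

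**Step 4: PD cut-off read as 50% of evaluable patients.** Let N ~ Bin(18, 1 − f) be the number evaluable, and average P(Bin(N, p) ≥ N/2, rounded up) over N. At f = 5% / 10%, power is 96.9% / 96.5% and the false positive rate is 1.8% / 2.1%.

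**Step 5: reference group.** The expected loss is 15f = 0.75 or 1.5 patients. With 13 patients the 90.0% becomes 87.5%; a loss of 2 is somewhat above expectation at either rate.

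**The case against.** The strongest reply is that the event may be rare and the harm mild. Histology is checked per specimen, 500 mg of enhancing tissue is required, and Section 9.5.5 asks for only 50 mg to measure drug. One failed specimen need not lose the patient. Even on the harsher reading, a 10% failure rate leaves every power figure above 90%, and false positive rates fall. All of this stands, and it limits the weight of the point.

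It is also fair that the PD loss in Step 3 depends on a reading that Section 11 does not spell out. Under the 50% reading PD power hardly moves, although its false positive rate is then no longer fixed at the stated value. Likewise, Section 9.5.5 speaks of eight tumour samples at the interim, which presumes eight results rather than failures filled in for missing ones. Independence of histology failure from outcome is an assumption too.

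A reader might infer that patients are replaced for nothing except absence of tumour. The documents do not support that: tissue mass, freezing time, slides or block, blood samples, doses and timing are all triggers. The gap concerns tumour content alone. A reader might also infer that the trial is underpowered or its false positive rate inflated. With no failure rate given, the first cannot be shown. The second does not occur with fixed counts, and under the 50% reading the change is 0.1 points at an assumed 10%.

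A study team might treat tissue that fails histology as containing no tumour, but the text does not say so.

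**Conclusion.** The mismatch is real on the text: a patient can lose both co-primary results and still not be replaced. The stated operating characteristics are correct for 8, 18 and 15 evaluable patients, but the replacement rules do not secure those numbers. At assumed failure rates of 5% to 10%, independent of outcome, the effect is small to moderate. It consists of about 2 to 7 points of PD power against the exact 97.9% if counts are fixed (about 1 point on the 50% reading), about 1 to 4 points of PK power against the exact 98.5%, and a wrongful futility stop of 2.0% to 3.4%. This is a cheap improvement that should be made, not a flaw that undermines the design.

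**What to change.** 1. **Section 9.5.** Replace the tumour-content trigger with: *no contrast-enhancing frozen specimen with tumor cell content >80% on central H&E review*. Section 9.5.4 already places this review before the specimen is split, so the decision precedes that patient's PK and PD results.
2. **Section 11.** Apply 3 of 8, 8 of 18, 9 of 18 and the reference size of 15 to evaluable (not replaced) patients, and state that 9 of 18 is a count. The published operating characteristics then stand unchanged, and the interim waits for 8 evaluable patients.
3. **Timing.** Run H&E review during accrual and keep the PD assay in a single batch. Limit the Section 11 sentence on simultaneous sample processing to lysis and the PD assay. Section 9.5.5 already needs patients 1 to 8 reviewed and split first.

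Reduced cut-offs for a shortfall are not needed once replacement is in place, and they would depart from the stated design. PD 8 of 16 has a 2.7% false positive rate (stated 2%), and PD 9 of 17 has 96.0% power (stated 98%).

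**Cost.** Wording edits, plus replacements. At an assumed 5% / 10%, expected enrolment is 33/0.95 = 34.7 or 33/0.90 = 36.7, so about 2 or 4 extra patients. In Group A it is 18/0.95 = 18.9 or 18/0.90 = 20.0, so about 1 or 2 extra patients given pre-operative drug. At 3 patients per month this adds about 0.6 or 1.2 months.

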### 9.5.1 Tissue Requirements for Protocol Surgery: Group A and Reference Group

Every effort should be made to collect adequate amounts of tissue.

The minimum **tissue requirements** to be collected from participants at the time of surgery include:

- 500 mg of fresh frozen tissue from the contrast enhancing portion of the tumor. This sample will be used for the determination of the primary objectives of the study for both the tumor drug distribution endpoints ([Section 9.5.5](#)) and EGFR phosphorylation endpoints ([Section 9.5.6](#))
- 100 mg of fresh frozen tissue from the non-contrast enhancing portion of the tumor (if low risk of inducing neurological injury). This sample will be used in an exploratory fashion regarding tumor drug distribution and EGFR phosphorylation.
- If sufficient tissue is available, 500 mg or more of additional enhancing tissue (for tumor sphere cultures)

The **remainder of the sample** should be fixed in formalin and processed for routine paraffin embedding and sectioning at the site, per usual site protocols in pathology.

The precise location in the tumor from which these specimens were obtained and the precise time should be recorded. Depending on local site's capabilities, if a common navigation system is used for surgical localization, segmentation of the tumor using 3D visualization software is recommended for accurate sampling localization. Using this

reconstructed model, a representative screenshot is requested demonstrating the location of the resected tissue. If not possible, then a screenshot of the MRI showing the location of the resected tissue should be included.

### **9.5.2 Archived and Protocol Surgery Paraffin Tumor Tissue (Group A and Reference Group)**

Prior to registration (Integral Biomarker): Archived tumor tissue from the most recent prior resection of high-grade glioma (pre-treatment) will be collected from all patients who are being screened for enrollment. **Evidence of EGFR amplification from this analysis will be considered a necessary inclusion criteria for enrollment.** EGFR gene amplification must be determined through a CLIA-certified FISH assay. Results of the EGFR-FISH assay must be sent to the ABTC Central Office to confirm patient eligibility. Determination of EGFR gene dosage through next-generation sequencing assay will not suffice for patient eligibility.

After completion of protocol surgery: 20 consecutively cut unstained slides each from the archived sample and the protocol surgery will be requested for exploratory IHC analysis including KI67 Analysis. These can be shipped together in separate containers along with the associated pathology report from the institution of collection. Notification of the delivery must be made by e-mail to both [name] (email: [contact]) and [name] (e-mail: [contact]). Include the name of the courier and the tracking no. in the email.

Please ship to:

[name]  
Memorial Sloan Kettering Cancer Center  
[name]  
[name]  
[name]  
Telephone: + 1 [contact]  
Fax: + 1 [contact]

### **9.5.3 Plasma Pharmacokinetics: Group A Participants**

Obtaining single plasma samples before and after the surgical procedure will allow the average drug concentration in plasma during the surgical procedure to be calculated. The pretreatment baseline plasma sample is needed to document that there are no potential compounds that could interfere with the detection of the drug in plasma or tumor samples. Obtaining these plasma samples is an important component of the drug distribution study and it does not have an additional objective per se. Samples are not being collected to characterize the pharmacokinetic behavior of the drug.

A single blood sample will be obtained at baseline, prior to the first dose of lapatinib. In addition, single blood samples will be obtained on the day of surgery at convenient times, both shortly before and shortly after the tumor resection.

For all pharmacokinetic plasma samples, draw 3 mL of blood into a plastic plasma collection tube with spray-coated sodium heparin at each of the time points specified. Promptly mix the specimen by gently inverting the collection tube several times and then place it on wet ice. Centrifuge the sample at 1,100-1,300 x g for 10 min at 4°C within 5-10 min after collection. Remove the plasma from the blood cells using a pipette and distribute it in equal volumes into two self-standing polypropylene cryogenic tubes with external threads. Affix a computer-printed label (protocol no., patient no., sample no., scheduled sample time) to each cryotube. Completely cover the label with protective cryogenic freezer tape (Fisher catalog no. 11-867B). Place the tubes on crushed dry ice until stored in a freezer maintained at -70°C.

The concentration of lapatinib in study samples will be determined by the ABTC Pharmacokinetics Center using an LC-MS/MS assay. The analytical method will be validated and applied to the analysis of study samples as recommended by the FDA Guidance for Industry: Bioanalytical Method Validation, May 2001 (<http://www.fda.gov/downloads/Drugs/Guidances/ucm070107.pdf>).

Send complete sets of plasma samples from each patient by overnight courier to the address listed below. Place the sample tubes within a zip lock plastic bag. Fill a seamless styrofoam container with at least 3 inches of dry ice, place the plastic bag containing the samples on top of the dry ice, and completely cover the bag with an additional 3 inches or more of dry ice. Seal the styrofoam container within a tight-fitting cardboard shipping box. Seal a copy of the sample collection time form for each set of samples within a zip-lock plastic bag and place the bag on top of the styrofoam container before the external shipping box is sealed. Send the samples on a Monday, Tuesday, or Wednesday by overnight courier for delivery by 10:00 AM on the following day. Notification of the delivery must be made by e-mail to both [name] (email: [[contact]](mailto:[contact])) and [name] (e-mail: [[contact]](mailto:[contact])). Include the name of the courier and the tracking no. in the email.

Please ship to:

[name]  
Massachusetts General Hospital  
[name]  
[name]  
[contact]

